6.7 BASELINE, TIME WINDOWS AND CALCULATED VISITS

The baseline values of laboratory data and vital signs for safety analysis will be defined as the last values before first drug infusion or administration.

Time windows are defined in Section 6.1 of the CTP. Adherence to time windows will be checked at the RPM/database lock (DBL) meeting.

7. PLANNED ANALYSIS

In general, a set of descriptive statistics to be displayed for continuous variables in the clinical trial report will be as follows:

Non-pharmacokinetic variables:

For End-Of-Text tables, the set of summary statistics is: N, mean, standard deviation (SD), min, median, and max.

Tabulation of frequencies for categorical or categorised data will include all possible categories and display numbers of observations (subjects) with the percentage relative to the respective treatment sequence / regimen. Percentages will be rounded to one decimal place. The category 'missing' will be displayed if and only if there are actually missing values. Percentages will be based on all subjects in the respective subject set whether they have non-missing values or not.

Pharmacokinetic variables:

The analysis of standard PK parameters will be performed according to [\(3\)](#).

7.1 DEMOGRAPHIC AND OTHER BASELINE CHARACTERISTICS

Only descriptive statistics by group are planned for this section of the report.

7.2 CONCOMITANT DISEASES AND MEDICATION

Concomitant diseases will be coded according to the most recent version of the Medical Dictionary for Regulatory Activities (MedDRA). Concomitant medication will be coded according to the most recent version of the World Health Organisation – Drug Dictionary.

A respective listing only is planned for this section of the report. The data will be summarised in total.

The relevance of the concomitant therapies to the evaluation of PK will be decided no later than at the RPM/DBLM.

A medication will be considered concomitant to a treatment, if it

- is ongoing at the time of first administration of this treatment, or
- starts within the analysis phase of the respective treatment (see [Section 6.1](#) for a definition of treatments and analysis phases).

7.3 TREATMENT COMPLIANCE

Treatment compliance will not be analysed as a specific endpoint. Any deviations from complete administration of the trial medication will be addressed in the RPM and described in the CTR.

7.4 PRIMARY ENDPOINT(S)

The analysis will be performed as defined in the CTP, Section 7.3.1.

7.5 SECONDARY ENDPOINT(S)

7.5.1 Key secondary endpoint(s)

There are no key secondary endpoints in this trial.

7.5.2 (Other) Secondary endpoint(s)

The analysis will be performed as defined in the CTP, Section 7.3.2.

Exclusion of PK parameters:

The ADS ADPP contains column variables APEXC and APEXCO indicating inclusion/exclusion (APEXC) of a PK parameter and an analysis flag comment (APEXCO). All analyses based on the PKS are based on PK parameter values which are not flagged for exclusion, i.e. with APEXC equal to "Included".

Exclusion of plasma concentrations:

The ADS ADPC (PK concentrations per time-point or per time-interval) contains column variables ACEXC or ACEXCO indicating inclusion/exclusion (ACEXC) of a concentration and an analysis flag comment (ACEXCO). Exclusion of a concentration depends on the analysis flag comment ACEXCO. For example, if ACEXCO is set to "ALL CALC", the value will be excluded for all types of analyses based on concentrations. If ACEXCO is set to "DESC STATS" the value will be excluded from descriptive evaluations per planned time point/time interval. If ACEXCO contains the addition "TIME VIOLATION" or "TIME DEVIATION", the value can be used for further analyses based on actual times. If ACEXCO is set to "HALF LIFE", the value will be excluded from half-life calculation only; the value is included for all other analyses.

Further details are given in [\(3, 4\)](#).

7.7 EXTENT OF EXPOSURE

A respective listing only is planned for this section of the report.

7.8 SAFETY ANALYSIS

The analysis will be performed as defined in the CTP. All safety analyses will be performed on the TS.

7.8.1 Adverse events

AEs will be coded with the most recent version of MedDRA. The analyses of AEs will be descriptive in nature. All analyses of AEs will be based on the number of subjects with AEs and not on the number of AEs.

For analysis, multiple AE occurrence data on the eCRF will be collapsed into one event provided that all of the following applies:

- All AE attributes are identical (lower level term, intensity, action taken, therapy required, seriousness, reason for seriousness, relationship, outcome, AE of special interest (AESI))
- The occurrences were time-overlapping or time-adjacent (time-adjacency of two occurrences is given if the second occurrence started at most 1 hour after the first occurrence ended)

The following are considered as AESIs in this trial:

- Hepatic injury, as defined by the following alterations of hepatic laboratory parameters:
 - an elevation of AST and/or ALT ≥ 3 -fold ULN combined with an elevation of total bilirubin ≥ 2 -fold ULN measured in the same blood sample, and/or
 - marked peak aminotransferase (ALT, and/or AST) elevations ≥ 10 fold ULN

For further details on summarisation of AEs data, please refer to ([5](#), [6](#)).

According to ICH E3 ([7](#)), AEs classified as ‘other significant’ need to be reported and will include those non-serious with

- (i) ‘action taken = discontinuation’ or ‘action taken = reduced’, or

(ii) marked haematological and other lab abnormalities or lead to significant concomitant therapy as identified by the Clinical Monitor/Investigator at a RPM/DBLM.

An overall summary of AEs will be presented.

The frequency of subjects with AEs will be summarised by group, primary system organ class (SOC) and preferred term (PT) (MedDRA levels to be displayed in the tables).

Separate tables will be provided for subjects with other significant AEs according to ICH E3 ([7](#)), for subjects with drug-related AEs, for subjects with significant non-serious AEs (only if these were defined for the project) and for subjects with serious AEs.

For disclosure of AE data on ClinicalTrials.gov, the frequency of subjects with non-serious AEs occurring with an incidence of greater than 5 % (in preferred terms) will be summarised by treatment, primary SOC and PT. The frequency of subjects with SAEs will also be summarised.

The SOCs will be sorted by default alphabetically. PTs will be sorted by frequency (within system organ class).

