4.1.5 Blinding and procedures for unblinding

4.1.5.1 Blinding

The trial is designed double-blind with regard to the subjects and the investigators (as well as the research staff at the trial site) in order to eliminate observer or performance bias. This means avoiding systematic differences in assessments regarding the subject's treatment (active or placebo). According to the rising dose design, the current dose level will be known to subjects and investigators. The trial will only be unblinded to the subjects, investigators and trial site staffs after locking of the database. Sponsor staffs that have direct interaction with the investigator and site staff (e.g. CML and CRA) will not be aware of the treatment allocation (i.e. active vs placebo) as well until database lock.

Monitoring on drug accountability should be conducted by unblinded CRA.

Regarding the sponsor, the database of this trial will be handled open-label, meaning that the trial functions of the sponsor are unblinded (including clinical monitor, data manager, statistician, bioanalyst, pharmacokineticist, pharmacometrist as well as dedicated CRO personnel). The objective of the trial is not expected to be affected.

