6.2 IMPORTANT PROTOCOL VIOLATIONS

Data discrepancies and deviations from the CTP will be identified for all subjects in the database (i.e., treated subjects and subjects with serious AE (SAE) which the investigator considered related to the screening procedure). Consistency check listings (for identification of violations of time windows) and a list of protocol deviations (e.g. deviations in drug administration, in blood sampling times, etc.) will be provided to be discussed at the report planning meeting (RPM). At this meeting, it will be decided whether a discrepant data value can be used in analyses or whether it must be corrected in the clinical database.

Each protocol deviation must be assessed to determine whether it is an important protocol violation (PV). For definition of important PVs, and for the process of identification of these, refer to the Boehringer Ingelheim reference document 'Protocol Violation Handling Definitions' [\(1\)](#).

If any important PVs are identified, they are to be summarised into categories and will be captured in the RPM minutes via an accompanying Excel spreadsheet [\(2\)](#). The following table contains the categories which are considered to be important PVs in this trial. If the data show other important PVs, this table will be supplemented accordingly by the time of the RPM. If substantial numbers of PVs are reported at the RPM, a decision about summarising the PVs in a tabular format will be made. Otherwise, only a PV listing will be provided.

The following [Table 6.2: 1](#) gives the important PVs for this trial.

Table 6.2: 1 Important Protocol violations

Category	Description
/ Code	
A	Entrance criteria not met
A1	Inclusion criteria violated
A2	Exclusion criteria violated
B	Informed consent
B1	Informed consent not available
B2	Informed consent too late
C	Trial medication and randomisation
C1	Incorrect trial medication administered
C2	Randomisation not followed
C3	Non-compliance
C4	Medication code broken inappropriately
C5	Incorrect administration of trial medication
D	Concomitant medication
D1	Prohibited medication use
E	Missing data
E1	Certain violations of procedures used to measure primary or secondary data
F	Incorrect timing
F1	Certain violations of time schedule used to measure primary or secondary data.

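### SAP 7.8.1 allows an unblinded clinical monitor to select 'other significant' AEs by judgement for one by-treatment table, although a blinded investigator is available to do it

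*SAP*

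**What the plan says.** SAP 7.8.1 follows ICH E3 in reporting 'other significant' non-serious AEs and defines them by two routes. Route (i) reads off the recorded action taken: "action taken = discontinuation" or a reduction. Route (ii) covers "marked haematological and other lab abnormalities or lead to significant concomitant therapy as identified by the Clinical Monitor/Investigator at a RPM/DBLM". The section then promises a separate table of subjects with such events, and SAP 6.1 says that AE displays account for treatment, with all placebo subjects pooled.

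Protocol 4.1.5.1 sets out who knows the allocation:

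- Sponsor: the database is handled open-label, and "the trial functions of the sponsor are unblinded (including clinical monitor, data manager, statistician" and several further roles are named.
- Site: "The trial will only be unblinded to the subjects, investigators and trial site staffs after locking of the database".
- Local monitoring staff: "Sponsor staffs that have direct interaction with the investigator and site staff (e.g. CML and CRA) will not be aware of the treatment allocation" until database lock.

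The same section adds a general statement that the trial's objective is not expected to suffer from the sponsor being unblinded.

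**The concern.** The protocol justifies the double blind as a way to avoid systematic differences in assessment between active and placebo. Route (ii) is an assessment, because someone has to decide whether a laboratory abnormality is marked or a concomitant therapy significant. The SAP gives that decision to either of two roles, and one of them knows who received active drug. A borderline event could then be more or less likely to be labelled depending on the arm it came from, and the resulting counts would stand side by side by treatment.

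Safety is described and not tested in this trial, so readers rely on the tabulated counts. How a subject enters a table should therefore not depend on allocation when that can easily be avoided.

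**Working it through.** The plan states no figure to reproduce for this point. The check sets the passages side by side, with one calculation for scale.

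1. **Is the rule mechanical?** Route (i) is: it uses a recorded field. Route (ii) is not: SAP 7.8.1 gives no cut-off for either of its two qualifying words. The same section does define hepatic AESIs numerically (3-, 2- and 10-fold ULN).

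2. **Who decides, and when?** The wording is "as identified by the Clinical Monitor/Investigator at a RPM/DBLM". The slash allows either role. The meeting probably precedes lock, since SAP 6.2 lets the report planning meeting require a value to be corrected in the clinical database. If so, the investigator is still blinded at that point under Protocol 4.1.5.1, and the clinical monitor is not.

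3. **Which monitor is meant?** Protocol 4.1.5.1 separates the clinical monitor (unblinded) from the local monitor and the CRA (blinded). The SAP uses the name of the unblinded role.

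4. **Where does the selection go?** It goes into a separate table (SAP 7.8.1), displayed by treatment (SAP 6.1). Protocol 7.3.3 spoke only of a separate listing.

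5. **How much of the table rests on route (ii)?** Each subject receives a single dose (Protocol 4.1.4), so discontinuation or reduction can seldom apply beyond a stopped infusion. Route (ii) is likely to be the main way in.

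6. **Is there a safeguard?** Neither document requires the blinded role to decide, or the review material to be free of treatment codes.

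7. **Scale.** Inputs: 6 active and 2 placebo subjects in each of 4 dose groups (Protocol 3.1), with placebo pooled (SAP 6.1).
   - Pooled placebo: 4 × 2 = 8 subjects.
   - One subject in or out of an active group: 1/6 = 16.7 percentage points.
   - One subject in or out of pooled placebo: 1/8 = 12.5 percentage points.

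8. **What does not depend on the selection?** Causality is determined by the investigator (Protocol 5.2.2.2), who is blinded until lock, so the primary endpoint (subjects with drug-related AEs) is untouched. All AEs are tabulated by treatment, system organ class and preferred term (Protocol 7.3.3, SAP 7.8.1). Laboratory changes from baseline and shifts against reference ranges are reported separately (SAP 7.8.2).

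**The case against.** The strongest case against is that the label cannot create, hide or alter an AE. It marks a subset of events already recorded at a blinded site, and a reader can compare the subset with the full AE and laboratory tables. Sponsor unblinding is openly declared in an exploratory Phase I trial without hypothesis tests. The company standards that the SAP cites for AE and laboratory handling may define a marked abnormality. The meeting probably takes place before lock, so part of the remedy may already be practice.

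Most of this stands, and it limits the point to one descriptive table. It does not remove the point. The protocol's general reassurance does not address classification of AEs by sponsor staff. The cited standards are not available here, so the claim is only that the SAP text itself gives no threshold. Earlier timing keeps the investigator blinded but does nothing about the clinical monitor.

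A reader might also extend the concern to SAP 6.2, where "At this meeting, it will be decided whether a discrepant data value can be used in analyses". The text does not support that. The section deals with data discrepancies and protocol deviations such as sampling times and drug administration. It does not mention classification of AEs and does not say who decides.

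**Conclusion.** The point holds as a minor one. Entry into the table of other significant AEs may be decided by someone who knows the allocation, on terms that the SAP text leaves to judgement. 'May' is the right word, because the SAP equally permits the blinded investigator to decide.

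A reader might infer that the blind is defeated for the safety assessment, or that 16.7 and 12.5 points measure a bias. Neither follows. The blinded recording and causality assessment underneath are intact, and any single subject moves any row by that much in groups this small. The documents give no basis for estimating how many borderline events there would be, so the size of any bias is unknown.

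The conclusion assumes that the SAP's 'Clinical Monitor' is the role that Protocol 4.1.5.1 calls unblinded. If the blinded local monitor was meant, the concern falls away, and the SAP should say so.

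**What to change.** Add one sentence to SAP 7.8.1: route (ii) events are selected by the blinded investigator, from listings that carry no treatment codes, and the selection is documented before database lock. The sponsor's clinical monitor may propose candidates from the same uncoded listings but does not decide. This keeps sponsor medical input while taking knowledge of allocation out of the decision.

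The cost is one extra sign-off, preparation of uncoded listings, and slightly less sponsor control over the classification. No new data, subjects or procedures are needed. Writing down in advance what counts as marked or significant, or citing the standard that defines it, would also help but is not essential.

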7.8.2 Laboratory data

The analyses of laboratory data will be descriptive in nature and will be based on BI standards ([8](#)), descriptive statistics with original values will be provided by group for baseline, on-treatment values and for changes from baseline. Clinically relevant findings in laboratory data were to be reported as AEs and will be analysed as part of AE analysis. Laboratory values will be compared to their reference ranges and frequency tables will be provided for the number of subjects within and outside the reference range at baseline and the last measurement on treatment. Frequency tables for categorical laboratory values categorised by value at baseline and last value on treatment will be shown.

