5.2.4.2 Continuous ECG monitoring

Cardiac rhythm (including heart rate) will be monitored by means of continuous 12-lead ECG recording for at least 15 min before (for baseline assessment) and 2 h following drug administration.

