5.2.5.2 Medical examinations

At the screening visit, the medical examination will include documentation of subject information, informed consent, demographics including height and body weight, smoking and alcohol history, relevant medical history and concomitant therapy, review of inclusion and exclusion criteria, review of vital signs (BP, PR), 12-lead ECG, laboratory tests, and a physical examination. At the end of trial examination, it will include review of vital signs, 12-lead ECG, laboratory tests, and a physical examination with determination of weight

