6. INVESTIGATIONAL PLAN

6.1 VISIT SCHEDULE

Exact times of measurements outside the permitted time windows will be documented. The acceptable time windows for screening, observation visit, and end of trial examination are given in the Flow Chart.

Study measurements and assessments scheduled to occur 'before' trial medication administration on Day 1 are to be performed and completed within a 2 h-period prior to the trial drug administration (including blank values for PK).

The acceptable deviation from the scheduled time for vital signs and ECG will be:

- ± 15 min up to including 12 h
- ± 30 min from 12h up to including 48 h
- ± 60 min from 48 h up to Day 8
- ± 24 h from Day 15 up to Day 71
- ± 48 h on Day 92
- ± 72 h from Day 120 up to the last measurements

The tolerance for pharmacokinetic/ADA/laboratory parameters will be:

- ± 1 min up to including 1 h
- ± 5 min up to including 12 h
- ± 15 min up to including 48 h
- ± 60 min from 48 h up to Day 8
- ± 24 h from Day 15 up to Day 71
- ± 48 h on Day 92
- ± 72 h from Day 120 up to the last measurements

If scheduled in the [Flow Chart](#) at the same time as a meal, blood sampling, vital signs and 12-lead ECG recordings have to be done first. Furthermore, if several measurements including venipuncture are scheduled for the same time, venipuncture should be the last of the measurements due to its inconvenience to the subject and possible influence on physiological parameters.

For planned individual plasma concentration sampling times refer to the Flow Chart. While these nominal times should be adhered to as closely as possible, the actual sampling times will be recorded and used for determination of pharmacokinetic parameter.

If a subject misses an appointment, it will be rescheduled if possible. The relevance of measurements outside the permitted time windows will be assessed no later than at the Report Planning Meeting.

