6.2.3 End of trial and follow-up period

For AE assessment, laboratory tests, collection of PK and ADA samples, recording of ECG and vital signs, and physical examination during the end of trial period, see [Sections 5.2.2](#) to [5.2.5](#).

Subjects who discontinue treatment before the end of the planned treatment period should undergo the end of trial visit.

All abnormal values (including laboratory parameters) that are judged clinically relevant by the investigator will be monitored using the appropriate tests until a return to a medically acceptable level is achieved. Adverse events persisting after trial completion must be monitored until they have normalised or have been sufficiently characterised.

The end of the trial as a whole is defined by the 'last regular visit completed by last subject' or 'end date of the last open AE' or 'date of the last follow-up test' or 'date of an AE has been decided as sufficiently followed-up', whichever is latest.

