7.3.3 Safety analyses

Safety will be assessed for the endpoints listed in [Section 5.2.1](#). All treated subjects (that is, all subjects who received at least one dose of study drug), will be included in the safety evaluation. Safety analyses will be descriptive in nature and will be based on BI standards. No hypothesis testing is planned.

Treatments will be compared in a descriptive way. The placebo control group in the safety evaluation will consist of all placebo treated subjects, regardless of the dose group in which they were treated. The active treatment groups will be compared to the placebo group in a descriptive way. Tabulations of frequencies/proportions will be used for the evaluation of categorical (qualitative) data, and tabulations of descriptive statistics will be used to analyse continuous (quantitative) data.

Measurements (such as vital signs, or laboratory parameters) or AEs will be assigned to treatments (see [Section 4.1](#)) based on the concept of treatment emergent AEs. Therefore, measurements planned or AEs recorded prior to first intake of trial medication will be assigned to 'screening', those between first trial medication intake until the end of trial visit will be assigned to the treatment period, and those after the end of trial examination will be assigned to 'post-study'. These assignments including the corresponding time intervals will be defined in detail in the TSAP.

Adverse events will be coded using the Medical Dictionary for Regulatory Activities (MedDRA). Frequency, intensity and causal relationship of AEs will be tabulated by treatment, primary system organ class and preferred term. SAEs, AESIs (see [Section 5.2.2.1](#)) and other significant AEs (according to ICH E3) will be listed separately.

Laboratory data will be compared to their reference ranges. Values outside the reference range will be highlighted in the listings. Additionally, differences from baseline will be evaluated.

Vital signs or other safety-relevant data observed at screening, baseline, during the course of the trial and at the end-of-trial examination will be assessed with regard to possible changes compared to findings before start of treatment.

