6. GENERAL ANALYSIS DEFINITIONS

6.1 TREATMENT(S)

For basic study information on investigational products, assignments of treatment, and selection of doses, please see CTP, Sections 3 and 4.

All subjects on active treatment will be analysed according to their actual treatment group. All placebo subjects will be analysed in one pooled placebo group (i.e. no distinction between dose groups will be made).

The following separate study phases will be defined for analyses of adverse events (AEs), laboratory tests, and vital signs:

- **Screening** (ranging from 0:00 h on day of informed consent until first administration of study drug)
- **On-treatment** (separately for each treatment, ranging from the time of first administration of the respective treatment until study termination date)

Displays of AEs, laboratory tests and vital signs will account for the treatments ([Table 6.1: 1](#)) during on-treatment phase.

A) High-level analysis (for CTR Section 15.3 and Appendix 16.1.9.2.8.2 displays)

In this analysis screening and post-study periods will not be included. In Section 15.3 AE tables (but not in Appendix 16.1.9.2.8.2 AE tables), the following totals will be provided in addition to the by treatment display:

- a total over all active treatments during on-treatment phase, excluding placebo ("Total BI")
- a total over the on-treatment phase and placebo ("Total")

B) Low-level analysis (for Appendix 16.1.9.2.8.1 displays)

Results will be presented separately for the following phases:

- Screening
- On-treatment (labelled with the name of the study drug administered at the start of the on treatment phase)

In Section 16.1.9.2.8.1 AE tables, the following totals will be provided in addition:

- a total over all active treatments during on-treatment phase, excluding placebo ("Total BI")
- a total over all phases ("Total")

Table 6.1: 1 Treatment Set-up

	Treatment	Short label
A	BI 655130, [REDACTED] iv	[REDACTED] iv
B	BI 655130, [REDACTED] iv	[REDACTED] iv
C	BI 655130, [REDACTED] iv	[REDACTED] iv
I	Placebo, iv	Placebo
D	BI 655130, [REDACTED] sc injection	[REDACTED] sc
S	Placebo, sc injection	Placebo

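### Cheap improvement, not an error: both laboratory frequency tables in SAP 7.8.2 use only baseline and the last on-treatment value, normally the Day 148 sample, so they show recovery rather than occurrence

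*SAP*

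**What the plan says.** SAP 7.8.2 plans two laboratory frequency displays. For the reference range, "frequency tables will be provided for the number of subjects within and outside the reference range at baseline and the last measurement on treatment". For categorical tests, "Frequency tables for categorical laboratory values categorised by value at baseline and last value on treatment will be shown". The same section plans by-group descriptive statistics for baseline, on-treatment values and changes from baseline. It states that laboratory analyses follow the sponsor's standards, citing reference 8.

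Three places settle which sample is the last on treatment:

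- SAP 6.1 defines the on-treatment phase as "ranging from the time of first administration of the respective treatment until study termination date".
- Protocol 7.3.3 assigns measurements in the same way: "those between first trial medication intake until the end of trial visit will be assigned to the treatment period".
- Laboratory tests belong to the final visit. Protocol 5.2.5.2 says "At the end of trial examination, it will include review of vital signs, 12-lead ECG, laboratory tests", and protocol 6.2.3 lists "laboratory tests, collection of PK and ADA samples, recording of ECG and vital signs, and physical examination during the end of trial period" without separating the intravenous and subcutaneous groups.

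Protocol 7.3.3 also plans to highlight out-of-range values in the listings. In general terms it calls for frequency tabulation of categorical data, and for assessment of changes in safety data over the course of the trial.

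**The concern.** This is a single-dose trial whose primary objective is safety and tolerability, described for each active dose group against pooled placebo. A drug effect on a laboratory value could be expected soon after dosing and could then resolve. A table that compares baseline with the last sample months later will show such a subject as in range at both times. It answers whether an abnormality was still there at the end. A reader of a by-group table would usually first want to know how many subjects ever had one.

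At stake is the ease and reliability of one descriptive comparison. Without a stated count, a reader who wants to compare transient excursions between dose groups and placebo must count them by hand from listings for 32 subjects.

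**Working it through.** The plan states no figure to reproduce here. The check has four steps.

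**1. Which sample is the last on treatment?** The Flow Chart puts the end-of-trial visit at 3528 h, Day 148±3. 3528 / 24 = 147 days after the dose, and 147 / 7 = 21.0 weeks. This holds for completers without a later unscheduled test.

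The subcutaneous Flow Chart, as extracted from the PDF, shows no laboratory mark in its end-of-trial row. It does show an ECG-monitoring mark there, although protocol 5.2.4.2 limits monitoring to "continuous 12-lead ECG recording for at least 15 min before (for baseline assessment) and 2 h following drug administration". With the two protocol sections quoted above that place laboratory tests at the final visit, this points to a shifted column, not to a missing sample.

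**2. How many scheduled samples do the tables use?** The post-dose laboratory times are 4 h, 24 h, 72 h, 168 h (Day 8), 504 h (Day 22), 672 h (Day 29) and 3528 h, which makes 7. The tables use 1, so 6 of 7 (85.7%) enter neither. If an excursion lasted one visit and were equally likely at any of the 7, the last-value table would show it with probability 1/7 = 14.3%. The count is approximate: at 32 h the extracted intravenous chart has a mark under laboratory, while the subcutaneous chart has it under body temperature. That mark is not counted, and the conclusion does not depend on it.

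The last sample is also far from the one before: 148 − 29 = 119 days. Protocol 6.1 allows ± "24 h from Day 15 up to Day 71" and ± 72 h from Day 120, so the gap is 119 ± (1 + 3), or 115 to 123 days.

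**3. Where else does a transient out-of-range value appear?**

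| Output | What it shows | By-group count of subjects out of range at any time? |
|---|---|---|
| Highlighted listings (protocol 7.3.3) | Each individual value | No |
| Mean, SD, min, median, max and changes from baseline (SAP 7, SAP 7.8.2) | Extremes and average shifts by group | No |
| AE tables (protocol 5.2.2.2, SAP 7.8.1) | Findings judged clinically relevant | Only for those findings |
| Hepatic AESI (SAP 7.8.1) | Numerically defined marked liver changes | Only for those changes |
| General wording in protocol 7.3.3 | Frequency tabulation of categorical data; changes during the trial | Not specified |

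What remains uncounted in the SAP text is a transient excursion that was not judged an adverse event.

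**4. What would counting at any time cost in chance flags?** The documents give no out-of-range rate, so this step is an assumption: a two-sided 95% reference range, no drug effect and 7 post-dose looks.

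- Independent looks: 1 − 0.95^7 = 0.302 of subjects per analyte. Expected counts are 6 × 0.302 = 1.8 in an active group and 8 × 0.302 = 2.4 in pooled placebo.
- Normally distributed values with within-subject correlation 0.5 (simulation): about 0.23.
- Correlation 0.8 (simulation): 0.149, giving 6 × 0.149 = 0.9 and 8 × 0.149 = 1.2.
- One look: 0.05.

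Restricting to subjects in range at baseline gives 0.95 × 0.302 = 0.287 when looks are independent. It gives about 0.20 at correlation 0.5 and 0.11 at 0.8, so the baseline split helps mostly when correlation is high.

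Protocol Table 5.2.3: 1 has 6 + 5 + 3 + 6 + 9 + 5 = 34 routine quantitative analytes (haematology, automatic differential, coagulation, enzymes, substrates, electrolytes). Tests done only at screening or only on a trigger are left out. Expected chance flags per subject are 34 × 0.149 = 5.1 to 34 × 0.302 = 10.3, against 34 × 0.05 = 1.7 at one look. Counting relative and absolute differentials separately, and both prothrombin results, makes 34 + 5 + 1 = 40 analytes and 6.0 to 12.1 flags, against 2.0.

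**The case against.** The strongest reply is that the absence cannot be verified. SAP 7.8.2 delegates to an internal standard on the display and analysis of laboratory data, and that standard may already require any-time abnormality tables. This stands. The documents support only the statement that the SAP text does not specify such a count.

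Second, transient values are visible elsewhere, and those of clinical relevance are counted as adverse events. This also stands and is the main reason why severity is low. A reader might infer that transient abnormalities would go unreported; step 3 shows that they would not. A reader might also infer that the urine dipstick tests have no other by-group summary. Protocol 7.3.3 calls in general for frequency tabulation of categorical data, so that reading goes too far, although the protocol does not say at which times.

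Third, any-time counts in groups of 6 against 8 pool many chance flags. That is correct and is a real cost. It argues for reading the tables descriptively against placebo, where the same chance process operates. It does not argue for relying on a single sample 21 weeks after the dose.

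Fourth, not every categorical test has a worst direction, urine pH being the clear case. The fix allows for this.

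**Conclusion.** The point holds as a low-severity improvement. As written, the SAP's two laboratory frequency tables leave out about 6 of 7 scheduled post-dose times, including every scheduled sample from the first 28 days after dosing. They describe recovery or persistence at Day 148±3.

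A reader might take this as a contradiction or a safety failure, and the documents support neither. No section promises an any-time count. The primary endpoint (subjects with drug-related adverse events) is unaffected, dose escalation does not rest on these tables, and no hypothesis is tested.

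The conclusion assumes that completers have their end-of-trial laboratory sample in all four dose groups. It is limited by the fact that reference 8 could not be read. The chance-flag range of about 15% to 30% of subjects per analyte rests on the assumed 95% range and on within-subject correlation between 0.8 and 0.

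**What to change.** In SAP 7.8.2 add, by dose group and pooled placebo:

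- shift tables of baseline against the minimum, and baseline against the maximum, post-dose value relative to the reference range;
- shift tables of baseline against the worst post-dose category for ordered categorical tests, with urine pH handled by minimum and maximum.

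Keep the last-value tables and label them as a recovery display. State that the new tables are descriptive and are to be read against the 8 pooled placebo subjects. If reference 8 already requires these tables, cite it for that purpose in SAP 7.8.2 and add nothing else.

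The cost is a short SAP revision and standard programming on data already collected, with no protocol change. The drawback is more sparse tables and more chance flags, of the size given in step 4 of the working.
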